### 8.5.5 Baseline Descriptive Statistics

A table of clinically relevant baseline variables will be created using the methods described in section 8.5.1.1.

### 8.5.6 Planned Interim Analyses

There are no planned interim analyses. Results will be reported after all the patients reach the primary endpoint and then at 24 months.

### 8.5.7 Subgroup Analyses

The following subgroups will be evaluated for the primary and secondary endpoints:

- Patients treated with Embosphere Microspheres 100-300 $\mu$  vs. 300-500 $\mu$
- Comparison of procedure time for patients embolized with radial vs. femoral access
- Embolizations that were/were not performed using the PErFecTED technique
- Bilateral vs. unilateral embolizations

#### 8.5.7.1 Exploratory analyses

Descriptive statistics may be generated for the exploratory endpoints. Additional analyses may be performed based on the data collected. However, any analyses performed using the exploratory endpoint will be hypothesis-generating, and no conclusions will be drawn from the results of these analyses.

[REDACTED]

## 9 Device or Procedure-Related Adverse Events

A Device or Procedure-related adverse event is defined in this post market study as any event that began on or after the date of the PAE procedure and is considered related to the study procedure and/or device by the investigator. All related events must be reported in the case report form and followed until resolution.

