## 5 Eligibility Criteria

- Inclusion Criteria
  - Patient has signed informed consent
  - Patient age is 18 years or older at time of informed consent
  - Patient will undergo PAE with Embosphere Microspheres for the treatment of symptomatic BPH with LUTS
- Exclusion Criteria
  - Patient is unable or unwilling to provide follow-up information
  - Patient is undergoing PAE for reasons that do not include symptomatic BPH with LUTS
  - Any other reason the investigator deems cause for exclusion

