### 9.3 Device or Procedure-Related Serious Adverse Events

A device or procedure-related serious adverse event is defined in this post market study as any event that began on or after the date of the PAE procedure and is considered related to the study procedure and/or device by the investigator. A device or procedure-related adverse event will be considered serious if it meets one of the following criteria:

- Results in death
- Is life-threatening. Life-threatening means that the patient was at immediate risk of death from the reaction as it occurred, i.e., it does not include a reaction which hypothetically might have caused death had it occurred in a more severe form
- Requires in-patient hospitalization or prolongation of existing hospitalization. Hospitalization admissions and/or surgical operations scheduled to occur during the study period, but planned prior to study entry are not considered AEs if the illness or disease existed before the patient was enrolled in the trial, provided that it did not deteriorate in an unexpected manner during the trial (e.g., surgery performed earlier than planned)
- Results in persistent or significant disability/incapacity. Disability is defined as a substantial disruption of a person's ability to conduct normal life functions
- Is a congenital anomaly/birth defect
- Is an important medical event. An important medical event is an event that may not result in death, be life-threatening, or require hospitalization, but may be considered an SAE when, based upon appropriate medical judgment, it may jeopardize the patient or patient and may require medical or surgical intervention to prevent one of the outcomes listed in the definitions

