#### 9.4 Reporting of Serious Adverse Events

Any treatment-related SAE that occurs on or after the date of the PAE or worsened in severity or frequency after the PAE must be reported to the Sponsor immediately (not to exceed 24 hours within site notification of the event) in the case report form or via email. It is the responsibility of Investigators to inform their IRB/EC of complications or serious injury as required by their IRB/EC procedure and/or federal law. Merit Medical is responsible for relaying information about serious adverse events and/or treatment related adverse events to the other participating Investigators and regulatory bodies as required.

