## 18 Safety Medical Monitor

An independent safety medical monitor shall be responsible for systemic review and adjudication of specified events (e.g., all treatment-related adverse events and all deaths) . At a minimum, assess the reported event with the associated documented risks of device, vascular embolization, and PAE treatment.

Potential risk for Embosphere Microspheres:

- Immune reaction in patients who are hypersensitive to collagen or gelatin (careful consideration should be given prior to using this product in patients who are suspected to be allergic to injections containing gelatin stabilizers)

Potential risk for vascular embolization:

- Paralysis resulting from untargeted embolization or ischemic injury from adjacent tissue edema
- Undesirable reflux or passage of Embosphere Microspheres into normal arteries adjacent to the targeted lesion or through the lesion into other arteries or arterial beds, such as the internal carotid artery, pulmonary, or coronary circulations
- Pulmonary embolism
- Ischemia at an undesirable location, including ischemic stroke, ischemic infarction (including myocardial infarction), and tissue necrosis
- Capillary bed occlusion and tissue damage
- Vessel or lesion rupture and hemorrhage
- Vasospasm
- Recanalization
- Foreign body reactions necessitating medical intervention
- Infection
- Complications related to catheterization (e.g., hematoma at the site of entry, clot formation at the tip of the catheter and subsequent dislodgment, and nerve and/or circulatory injuries, which may result in leg injury)
- Allergic reaction to medications (e.g., analgesics)
- Allergic reaction o contrast media or embolic material
- Pain and/or rash, possibly delayed form the time of embolization
- Death
- Blindness, hearing loss, loss of smell, and/or paralysis

PAE specific potential complications:

- Non-targeted embolization of the rectum, bladder, scrotum, penis, or other areas
- The most frequent post-procedure complication includes “Post-PAE Syndrome,” which includes nausea, vomiting, fever, pelvic pain, burning sensation, dysuria, and frequent or urgent urination
- Skin burn (radiation exposure) from prolonged fluoroscopy time
- Blood in urine, semen, or stool
- Bladder spasm
- Hematoma at the catheter site
- Urinary tract infection
- Urinary retention
- Constipation

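### The AE and SAE definitions (sections 9 and 9.3) rest on onset alone while section 9.4 also covers worsening, so related worsening of urinary symptoms present at entry may be missed or counted inconsistently

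*Combined protocol and SAP*

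**What the plan says.** Three parts of section 9 of the combined protocol and SAP set the rules.

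- Section 9 defines a related adverse event as "any event that began on or after the date of the PAE procedure and is considered related to the study procedure and/or device". Worsening of an earlier condition is not mentioned.
- Section 9.3 opens its SAE definition with the same test, "any event that began on or after the date of the PAE procedure", and then treats seriousness as a property of an event that already qualifies: "A device or procedure-related adverse event will be considered serious if it meets one of the following criteria".
- Section 9.4 sets the expedited reporting duty for "Any treatment-related SAE that occurs on or after the date of the PAE or worsened in severity or frequency after the PAE".

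Two other sections show why the difference matters in this population. Section 5 makes LUTS a condition of entry: "Patient will undergo PAE with Embosphere Microspheres for the treatment of symptomatic BPH with LUTS". Section 18 describes Post-PAE Syndrome as the most frequent complication after the procedure and includes in it "dysuria, and frequent or urgent urination". Urinary retention is a separate item in the same list, with no frequency attached.

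The related-AE rate at post-procedure, 3, 12 and 24 months is a secondary endpoint (section 8.1.2). Section 8.5.3.2 refers its analysis to section 9.3, and section 8.5.4 summarises the related events that were collected.

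**The concern.** The condition that qualifies a man for the study overlaps with the harms the study is meant to count. In a man who already has frequency or urgency, a urinary reaction to PAE may show as more of the same symptom rather than as a new one. A definition that asks only when the event began gives the site no clear instruction for that man.

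At stake is the main safety summary of a single-arm study. There is no control group in which the same omission would occur and partly cancel. If sites apply different readings, differences in AE rates between sites or countries would partly reflect coding practice.

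**Working it through.** No arithmetic in the plan depends on this point, so the check is to apply each rule to the four kinds of related event.

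| Related event after PAE | Sections 9 and 9.3, literal reading | Sections 9 and 9.3, broad reading | Section 9.4 |
|---|---|---|---|
| New, not serious | AE | AE | not applicable |
| New, serious | SAE | SAE | report |
| Worsening of an earlier condition, not serious | not an AE | AE | not applicable |
| Worsening of an earlier condition, serious | not an SAE | SAE | report |

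1. The two readings differ only in the last two rows. On the literal reading, what must have begun after PAE is the condition. On the broad reading, the worsening is itself the event.

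2. In the last row the literal reading puts 9.3 and 9.4 in conflict: the site must report as an SAE something that the SAE definition does not contain.

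3. The wording of 9.4 gives the literal reading some support. An event that starts after PAE is already within its first limb. The second limb adds something only for a condition that was present earlier, and only if such a condition is not already covered.

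4. In the third row no worsening clause applies anywhere. Section 9.4 deals with serious events alone, so a non-serious aggravation of frequency or urgency is recorded or not according to how the site reads section 9.

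5. Onset dating is also open. Section 8.5.4 reports start date and duration for each AE, and section 8.5.1.5 places events before or after each reporting cutoff. No section says whether a worsened symptom starts when it first appeared or when it became worse.

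6. Other data capture worsening only in part. IPSS is collected at 3, 12 and 24 months but is not scheduled at 4 weeks (sections 6.3 and 6.4). Men with an indwelling catheter need not complete it (section 4). Changes in catheter use and BPH medication are collected from 4 weeks. None of these carries a relatedness judgment or enters the AE rate.

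7. Size: the documents give no frequency of post-PAE worsening and no indication of how sites will read section 9. For scale only, if all 500 men were enrolled and evaluable, each man whose only related event went unrecorded would lower the per-subject rate by 1/500 = 0.2 percentage points. The number of such men is unknown.

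**The case against.** The strongest reply is that section 9 speaks of events in general and does not require a symptom to be absent at baseline. An aggravation that starts after PAE can fairly be called an event that began after PAE. Other text leans the same way. Section 18 has the safety monitor assess reported events against a list that includes frequent or urgent urination, in men who all have LUTS. Section 9.2 judges relatedness by timing and known response pattern, which a worsening can satisfy. The planned-admission item in section 9.3 withdraws its exemption when a prior illness deteriorates unexpectedly. Section 9.4 can also be read as a reporting rule that presupposes an SAE already so classed, not as a rival definition.

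Much of this stands, and it rules out several stronger conclusions that a reader might draw:

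- That worsening is never an adverse event. No section says so. Exclusion follows only from the literal reading.
- That the AE rate is biased downward. An under-count is possible if some sites read section 9 narrowly, but the documents do not show that they will.
- That the 54 of 286 men with indwelling catheters in the background cohort (section 1) measure the problem. That is catheter use at baseline, not worsening or missed events.
- That many men have dysuria at entry. LUTS at entry does not establish this.

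What the reply does not remove is the mismatch itself. The plan names worsening where it wants it reported, leaves it out of both definitions, and gives sites no rule for choosing between the readings. The safety monitor's review is unlikely to repair this, because an event that a site does not record is unlikely to reach the monitor.

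**Conclusion.** The point holds as an inconsistency between sections 9 and 9.3 on one side and section 9.4 on the other, with a resulting ambiguity in the related-AE endpoint. On the literal reading, related worsening of a urinary symptom present at entry is outside the AE definition, and serious worsening is reportable but undefined as an SAE. On the broad reading, both count. The secondary AE rate may therefore be too low or may differ by site. The amount cannot be estimated from the documents.

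This rests on two assumptions: that some men will have related worsening of a symptom they already had, and that not all sites will adopt the broad reading. Both are plausible given the entry criterion and the complication list, but neither is demonstrated. The primary endpoint, IPSS at 12 months, does not depend on the AE definition. The sponsor should correct the wording.

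**What to change.** Use one onset rule in sections 9, 9.3 and 9.4: an event that began, or a pre-existing condition that worsened in severity or frequency, on or after the PAE date, and that the investigator judges related to the device or procedure. State that the onset of a worsened condition is the date the worsening started. Add an eCRF completion note that related worsening of a baseline urinary symptom is recorded as an AE.

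The cost is a sentence in each of the three sections and one form instruction. No visit, assessment or sample size changes. The reported AE rate may be somewhat higher. If enrolment has already started, sites should be told from which date the rule applies and whether earlier records are to be reviewed against it, so that the counts stay comparable over time.

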## 7 Patient Completion and Discontinuation

Patients will be informed that they have the right to withdraw from the study at any time for any reason, without prejudice to their medical care. The investigator also has the right to withdraw patients from the study for any reason. If a patient is withdrawn or discontinued from the study, the reason for withdrawal from the study will be recorded on the end of study form. These subjects will not be replaced.

A subject will be considered lost to follow-up if he fails to return for more than one scheduled visit and is unable to be contacted by the study site staff.

The following actions must be taken if a subject fails to return for a required study visit:

- The site will attempt to contact the subject and reschedule the missed visit within the allowable visit timeline and counsel the subject on the importance of maintaining the assigned visit schedule and ascertain if the subject wishes to and/or should continue in the study
- Before a subject is deemed lost to follow-up, the Investigator(s) or designees will make every effort to regain contact with the subject (where possible, 3 telephone calls and, if necessary, a certified letter to the subject's last known mailing address or local equivalent methods). These contact attempts must be documented

- Should the subject continue to be unreachable, he or she will be considered to have withdrawn from the study with a primary reason of lost to follow-up

If a patient receives any non-PAE BPH procedure other than biopsy after his study PAE he will be automatically discontinued from the study, and follow-up data will no longer be collected. BPH procedures that will automatically discontinue the patient include but are not limited to TURP, Urolift, microwave ablation, aquablation, laser therapy and non-Embosphere Microspheres PAE.

Patients requiring multiple PAE procedures:

- If a patient receives an additional PAE procedure with Embosphere Microspheres after the initial treatment, he will remain in the study, and the schedule for the follow-up evaluations will begin according to the date of the first PAE with Embosphere Microspheres procedure until the subject reaches a total of 24 months follow-up. End of study will be calculated based on first PAE procedure for 24 months.

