#### **8.1.2 Secondary Endpoints**

The following are the secondary endpoints:

- IPSS measured at 3, 12, and 24 months post-baseline
- Device or Procedure-Related Adverse event rate at post-procedure, 3, 12, and 24 months
- Technical Success defined as the successful embolization of the treated prostate gland
- Frequency of indwelling bladder catheter removal post PAE at 3, 12, and 24 months
- Number of patients and types of treatment for refractory or recurrent LUTS due to BPH post PAE at 3, 12, and 24 months
- Change from baseline in Sexual Health Inventory for Men (SHIM) at 12 months post-PAE.

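### Section 7 stops all data collection after a discontinuing BPH procedure, while Sections 9 and 9.4 require related adverse events to be followed and reported with no such cut-off

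*Combined protocol and SAP*

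**What the plan says.** Section 9 sets the general duty for device- or procedure-related events: "All related events must be reported in the case report form and followed until resolution". Section 9.4 requires related SAEs arising on or after the PAE to reach the sponsor within 24 hours of the site learning of them. It sets no last date and makes no exception for men who have left the study. Section 8.5.4 lists stop date, outcome and duration among the items to report for each event.

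Section 7 sets the discontinuation rule: "If a patient receives any non-PAE BPH procedure other than biopsy after his study PAE he will be automatically discontinued from the study". Once that happens, "follow-up data will no longer be collected". The examples of discontinuing procedures end with "laser therapy and non-Embosphere Microspheres PAE". Repeat treatment with the study device is handled differently: "If a patient receives an additional PAE procedure with Embosphere Microspheres after the initial treatment, he will remain in the study", with follow-up to 24 months from the first PAE.

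Section 8.1.2 makes two affected outcomes secondary endpoints: "Device or Procedure-Related Adverse event rate at post-procedure, 3, 12, and 24 months" and "Number of patients and types of treatment for refractory or recurrent LUTS due to BPH post PAE at 3, 12, and 24 months". Section 8.5.1.5 defines who is evaluable for an event rate at each time point. A man qualifies by an event on or before the cutoff, by follow-up at or after the window's lower limit, or by a consent-withdrawal or loss-to-follow-up date at or after that limit.

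**The concern.** Sections 7 and 9 do not refer to each other. A site with a man whose related event is unresolved when he has, say, a TURP is told both to follow the event to its end and to stop collecting data. Whichever instruction it obeys, it departs from the other, and different sites may choose differently.

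The stop is not random with respect to outcome. The listed procedures are treatments for BPH, so most men who meet the rule will presumably do so because symptoms persisted or came back. Section 18 lists urinary retention and non-target embolization among the complications of PAE, so a related event and a further procedure could plausibly fall in the same man. Safety follow-up after retreatment also depends on which retreatment was given: it continues after a repeat Embosphere PAE and ends after the others. Section 2 gives long-term safety as part of the study's goal, so a gap in 24-month safety data bears on its purpose.

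**Working it through.** The plan states no retreatment rate and no adverse-event rate, so there is no figure of its own to reproduce. The conflict is read from the text; the arithmetic only illustrates its size.

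**Step 1. The sections side by side, for a man with an open related event who has a discontinuing procedure**

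| Section | Instruction | Exception for this man |
|---|---|---|
| 9 | Follow the event to resolution | None |
| 9.4 | Report any related SAE, no end date | None |
| 8.5.4 | Report stop date, outcome, duration | None |
| 7 | Discontinue; collect no more follow-up data | None for an open event |

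Events before the procedure stay in the data, and the first route in Section 8.5.1.5 counts them. Two things are lost: the end of any event still open, and any related event that starts later.

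**Step 2. Men affected.** Inputs: a ceiling of 500 men (Sections 4 and 8.3) and an assumed 5-15% with a discontinuing procedure.

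- 0.05 × 500 = 25 and 0.15 × 500 = 75 men whose later safety follow-up stops.
- If 10-40% of them have a related event open at that moment (also assumed), 25 × 0.10 = 2.5 and 75 × 0.40 = 30, so roughly 3 to 30 men lose an event's outcome.

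**Step 3. Direction of bias in the 24-month rate.** Let r be the share discontinued, p0 the 24-month related-event risk in other men, p1 the risk in discontinued men, and f the share of discontinued men's first events seen before they leave. All discontinuations are taken to precede the 24-month window, and all other men to be fully followed.

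- Rate with full follow-up: (1−r)p0 + r·p1
- Observed rate over all enrolled: (1−r)p0 + r·p1·f
- Observed rate with the Section 8.5.1.5 denominator: [(1−r)p0 + r·p1·f] / [(1−r) + r·p1·f]

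The last denominator is smaller because protocol-mandated discontinuation is not one of the three routes. A man discontinued event-free before the window therefore drops out.

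Worked row, r = 10%, p0 = 20%, p1 = 40%, f = 0.5:
- full follow-up: 0.9 × 0.2 + 0.1 × 0.4 = 22.0%
- all enrolled: 0.18 + 0.02 = 20.0%
- Section 8.5.1.5: 0.20 / (0.90 + 0.02) = 21.7%

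| r | p1 | f | Full follow-up | All enrolled | Section 8.5.1.5 |
|---|---|---|---|---|---|
| 5% | 40% | 0.5 | 21.0% | 20.0% | 20.8% |
| 5% | 40% | 0.8 | 21.0% | 20.6% | 21.3% |
| 10% | 40% | 0.5 | 22.0% | 20.0% | 21.7% |
| 10% | 40% | 0.8 | 22.0% | 21.2% | 22.7% |
| 20% | 20% | 0.5 | 20.0% | 18.0% | 22.0% |
| 20% | 20% | 0.8 | 20.0% | 19.2% | 23.1% |

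Here p0 = 20% throughout, and r = 20% is included as a wide upper value. Over r = 5-20%, p1 = 20% or 40% and f = 0.5 or 0.8, with 500 men:
- first related events unseen, 500·r·p1·(1−f): about 1 to 20 men
- event-free men leaving the denominator, 500·r·(1−p1·f): about 17 to 90 men

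Over all enrolled men the rate falls below the full-follow-up value in every row. With the plan's denominator it can lie on either side.

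**The case against.** The strongest defence is that Section 7 concerns participation and the visit schedule, while Sections 9 and 9.4 are the specific safety rules. A site could read follow-up data as the scheduled evaluations and still pursue an open event. That reading is possible, but the stop in Section 7 is unqualified and nothing states which section prevails.

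Other points on that side carry weight:

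- Once a second procedure has been done, attributing a new event to the index PAE is harder, and ending follow-up there is a recognisable design choice. That argues for a flag on later events. It does not explain why an event already open should lose its outcome.
- Retreatment is itself a secondary endpoint, so these failures are not hidden.
- Kaplan-Meier display is available (Sections 8.5.1.7 and 8.5.4). Censoring at a procedure chosen because of poor response may be informative, however, so it does not settle the matter.
- Related-event rates are secondary and descriptive in a single-arm study whose primary endpoint is 12-month IPSS.

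Three stronger readings are tempting, and the documents do not support them. A reader might infer that the 24-month rate is biased in the device's favour; Step 3 shows that the denominator rule can push it up. A reader might infer that all 25-75 men lose an event outcome; only those with an unresolved event do. A reader might infer that these men had the worst safety results; retreatment suggests inadequate symptom relief, and nothing in the documents links it to worse device safety. Nor does every further procedure trigger the rule: biopsy and repeat Embosphere PAE are exempt.

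**Conclusion.** The point holds and should be fixed. The conflict between Section 7 and Sections 9 and 9.4 is in the text and depends on no assumed rate. If Section 7 is followed as written, the resolution of open related events and all later related events are lost in men selected largely by treatment outcome, and Section 8.5.4 cannot be completed for the open events.

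The size rests on assumptions: 25-75 men with truncated safety follow-up at 5-15% of a ceiling of 500, and a smaller number, depending on how many have an open event, who lose its outcome. In the rows shown, the 24-month rate under the plan's denominator ranges from 0.3 percentage points below the full-follow-up value (21.7% against 22.0%) to 3.1 above it (23.1% against 20.0%), so no direction can be claimed. The primary endpoint does not rest on this point.

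**What to change.** Reconcile Sections 7, 9 and 9.4 so that a discontinuing procedure ends IPSS evaluation of the index PAE but not the collection of related adverse events and SAEs. Follow open related events to resolution and record related events to 24 months from the first PAE. Carry the date of the other procedure as a flag in the adverse-event tables, so that events before and after it can be shown separately. Men who withdraw consent are unaffected. This concerns data collection only and takes no position on which procedure a man should receive.

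In Section 8.5.1.5, state how men discontinued for another procedure enter the denominator at each time point. In Section 7, reconcile the trigger's wording as a non-PAE procedure with its own listing of a non-Embosphere PAE.

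The cost is a protocol amendment with IRB/EC review (Section 13) in the participating countries, four of which are assumed in Section 8.3. There would also be some added contacts, since these men currently have no remaining visits; Section 6.6 already allows follow-up by phone or mail. Attribution after a second procedure will be less certain, which the flag makes visible but does not remove.
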